Primary measure/platelet aggregation - The primary measurement will be ADP-stimulated platelet aggregation as assessed by the commercially-available VerifyNow P2Y12 assay (Accriva Diagnostics). The assay read-outs are 1) PRU, platelet reactivity units (specific for P2Y12 receptors); 2) BASE, total platelet function despite P2Y12 receptor blockage; and 3) IPA, percent platelet P2Y12 inhibition calculated as  $[(\text{BASE} - \text{PRU}) / \text{BASE}] \times 100$ . Two reports involving patients on antiplatelet therapy with high residual platelet reactivity demonstrated an effect of statins on lowering platelet aggregation via the VerifyNow assay. In CAD patients treated with clopidogrel, the addition of atorvastatin for 30 days resulted in an absolute mean difference of  $102 \pm 54$  PRU compared to baseline, corresponding to a  $37 \pm 14\%$  IPA. In a separate study of CAD/diabetic patients treated with clopidogrel, the addition of atorvastatin for 30 days resulted in an absolute mean difference of  $106 \pm 75$  PRU compared to baseline, corresponding to a  $33 \pm 20\%$  IPA. Similar effect sizes and variabilities of statins on reductions in platelet aggregation were observed in type II

Step	Procedure
1	Venipuncture with G21 butterfly needle.
2	Collect 2 ml blood into sodium citrate tube as waste tube
3	Collect 3x2 mL blood into 3 Greiner Vacuette tubes containing 3.2% sodium citrate. For VerifyNow assays.
4	Collect 2x3 ml blood into 2 Greiner Vacuette tubes containing 3.2% sodium citrate. For platelet activation assays.
5	Collect 1x2 ml blood into Vacuette tube containing EDTA. For CBC assay.
6	Collect 2x2 ml blood for metabolic panel, lipid panel and TSH assays.
7	Collect urine for urinalysis.
8	Pregnancy test with stick assay.

hyperlipidemic patients using light transmittance aggregometry. The relative reductions were reported as  $30 \pm 23\%$  (pravastatin),  $19 \pm 16\%$  (atorvastatin), and  $22 \pm 22\%$  (simvastatin).

[figure not shown]

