The reference range for the VerifyNow assay in individuals not on antiplatelet therapy is 180-376 PRU. These data are continuous and normally distributed. Thus, means and standard deviations will be used to describe reductions in platelet aggregation. Based on reported literature indicating additional effects of statins on platelet function following 30-day vs shorter periods of treatment, we have revised our experimental design to have a primary endpoint of 30-day treatment. Within-group thirty day evolocumab treatment will be tested by one-group paired t-test (two-sided) using each subject as its own control (evolocumab treatment vs vehicle pre-treatment control). Between-group thirty day evolocumab treatment will be tested by standard two-group t-test (two-sided, evolocumab vs vehicle control group run in parallel). The sample size estimates have been run using one-group, paired t-test published data. Using PRU mean difference = 102, SD = 54, power = 0.8 and alpha = 0.05, we estimate 6 subjects. Since the effects of statins on platelet aggregation may be mediated by both LDL-lowering and non-LDL-lowering mechanisms, we can calculate the sample size based on 50% reduced mean difference (PRU = 51). Then, we estimate 11 subjects. An equal number of subjects will be required for the placebo group run in parallel. Target enrollment will include all patients screened; we estimate that 10% may not be eligible based on exclusion criteria and/or may not return for scheduled blood draws. Thus, for 80% power, the target enrollment is 24 subjects over two years.

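### The 80% power rests on the smaller of two PRU standard deviations the plan quotes; at the other, paired power with 11 subjects is 53–56%, and the between-group test reaches about 56% at best

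*Combined protocol and SAP*

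**What the plan says.** All of this is in the Combined protocol and SAP under Proposed studies.

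- **Sources on the trial's own assay (section B, primary measure).** Two reports in clopidogrel-treated patients are quoted. One, in CAD patients, gives a change of 102 ± 54 PRU. The other is introduced as "In a separate study of CAD/diabetic patients treated with clopidogrel, the addition of atorvastatin for 30 days" and gives 106 ± 75 PRU. Each is restated as IPA: 37 ± 14% and 33 ± 20%.
- **Sources on another assay.** Light transmittance aggregometry results follow, introduced with "Similar effect sizes and variabilities of statins on reductions in platelet aggregation were observed in type II" hyperlipidemic patients: 30 ± 23% (pravastatin), 19 ± 16% (atorvastatin) and 22 ± 22% (simvastatin).
- **Tests.** The within-group effect is to be "tested by one-group paired t-test (two-sided) using each subject as its own control". A two-sided two-group t-test of evolocumab against the parallel vehicle group is planned as well.
- **Sizing.** "The sample size estimates have been run using one-group, paired t-test published data". With 102 and SD 54, "power = 0.8 and alpha = 0.05, we estimate 6 subjects". Because statins may also act by non-LDL routes, the plan then says "we can calculate the sample size based on 50% reduced mean difference (PRU = 51"), and concludes "Then, we estimate 11 subjects". An equal placebo group is added and the enrolment target is 24 for 80% power.
- **Restatement (section C).** A total of 20 participants is said to give about 80% power at 0.05, with recruitment continuing until 22 complete data sets are obtained.

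**The concern.** The two PRU sources share the assay, the drug, the 30-day duration and the clopidogrel background. Their means nearly agree (102 and 106), but the second SD is 75/54 = 1.39 times the first. The plan uses the smaller SD without saying why. Its one safety margin, the 50% discount, is argued from mechanism and applies to the mean. Nothing allows for uncertainty in the SD, and once the mean has been halved, n = 11 only just reaches 80%.

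Sections B and C then state 80% without naming the test or the SD. A reader who takes that at face value could read a non-significant result as good evidence against an effect of the size the plan assumes, when on the plan's second PRU source a miss would be nearly as likely as a hit.

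**Working it through.** **Inputs (sections B and C).** Two-sided alpha 0.05; target power 80%; 11 per group; changes of 102 (SD 54) and 106 (SD 75) PRU; 50% discount on the mean. The ± values are read as SDs of within-subject change, as the plan itself reads the 54.

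**Formulas.** With d = mean change / SD, power comes from the noncentral t distribution:
- paired test: df = n − 1, noncentrality d√n;
- two-group test, n per arm: df = 2n − 2, noncentrality d√(n/2).

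**Step 1: the plan's figure.** d = 51/54 = 0.944 and n = 11 give noncentrality 0.944 × √11 = 3.13 on 10 df. Power is 80.6%, and 11 is the smallest n reaching 80%. For the undiscounted 102/54, n = 5 already gives 87.8%, and the stated 6 gives 95.4%. The plan's arithmetic is sound.

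**Step 2: the other PRU source, same test, same n.**

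| Effect / SD | d | Paired power, n = 11 | Paired n for 80% |
|---|---|---|---|
| 51/54 (plan) | 0.944 | 81% | 11 |
| 53/75 (106 halved) | 0.707 | 56% | 18 |
| 51/75 (only the SD changed) | 0.680 | 53% | 19 |

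**Step 3: section C's total of 20.** Split equally, that is 10 per arm. At 51/54 the paired power is then 76%.

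**Step 4: the between-group test, 11 per arm.** This assumes that the quoted SD applies to change in both arms.

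| Effect / SD | Noncentrality | Power |
|---|---|---|
| 51/54 | 0.944 × √5.5 = 2.21 | 56% |
| 53/75 | 0.707 × √5.5 = 1.66 | 35% |
| 51/75 | 0.680 × √5.5 = 1.59 | 33% |

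**Step 5: the remaining quoted figures, halved, paired, n = 11.**

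| Quoted figure | Halved d | Power |
|---|---|---|
| IPA 37 ± 14 | 1.321 | 98% |
| IPA 33 ± 20 | 0.825 | 69% |
| Aggregometry 30 ± 23 | 0.652 | 50% |
| Aggregometry 19 ± 16 | 0.594 | 43% |
| Aggregometry 22 ± 22 | 0.500 | 32% |

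**Step 6: without the discount.** At paired n = 11, 106/75 gives 98.8%, and the aggregometry pairs give 97.3%, 94.3% and 84.8%.

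**The case against.** The strongest defence is that the discount is a deliberate margin. Undiscounted, every quoted pair gives at least 85% paired power with 11 subjects. That is correct, and it limits the point: the shortfall appears only at the halved effect. But the halved effect is what the plan chose to set n, and the stated 80% is the power at that effect.

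A reader might infer from the whole list that the plan picked the most favourable of five sources and that its own data put power at 32–56%. The documents do not support that, for three reasons.
- The IPA restatement 37 ± 14% is more favourable than 102/54, and 33 ± 20% gives 69%, above the top of that range.
- Three of the five would be statin groups within one set of aggregometry results, not separate sources.
- Aggregometry is another assay. Its figures carry over only as standardised ratios, and the text does not show that the ± values are SDs of paired change.

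The word similar is also partly defensible. On the percentage scale, the SDs of 14 and 20 overlap with 16 to 23, and 33 is close to 30. It is loose for means of 19 and 22.

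Finally, the between-group shortfall at SD 54 does not depend on which source was chosen. It arises because the sizing was done for the paired test only. It still belongs here, since the 80% is stated without naming a test.

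**Conclusion.** The point holds in a limited form. There is no calculation error: 11 per group is right for a paired test at 51 PRU and SD 54. The unqualified 80% is the problem. On the plan's other PRU source, paired power with 11 evolocumab subjects is 56% (53% if only the SD changes). At section C's total of 20 it is 76% even with SD 54. The planned between-group test has about 56% at SD 54 and 33–35% at SD 75.

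These figures assume the plan's 50% discount and that ± denotes the SD of change. The between-group figures also assume the same SD of change in both arms. The conclusion does not need the aggregometry results, which point the same way but rest on more assumptions. On the IPA scale the second VerifyNow study also stays below 80%, at 69%. The consequence is for how the power is stated and how a null result is read; it does not by itself show that the trial must be larger.

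**What to change.** Keep the sample size and change the wording.

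1. In sections B and C, replace the single 80% with power by test and SD for the discounted effect. With 11 per arm: paired 81% at SD 54 and 53–56% at SD 75; between-group about 56% and 33–35%, with the assumption about SD in both arms stated. Bring section C's total of 20 into line with this (76% paired at SD 54).
2. Give the reason for using SD 54, or say that there was none beyond the choice of source.
3. Qualify the sentence on similar effect sizes and variabilities: say that it concerns another assay, in percentages, and that the ratios of mean to SD are lower than for the pair used.
4. Report the day 28 effect with its confidence interval, so that a non-significant result is read against the effects it can and cannot exclude.
5. If an SD is estimated from the day 7 and day 14 placebo samples, label it a likely lower bound for the SD of change. Those samples are one week apart and contain no variation in treatment response, so they should not be the only basis for a detectable difference.

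The cost is a few sentences and a less favourable stated power. No subjects, visits or assays are added.

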Statins may show antithrombotic properties. The PROVE-IT trial, a study to assess the impact of statins on acute coronary syndrome (ACS), demonstrated an early beneficial effect after 30 days of follow-up that significantly reduced the risk of death, MI or rehospitalization. A retrospective study of 1616 patients (PRISM) also showed significant reduction of the risk during 30 day follow-up in ACS patients with statin therapy. Additional human studies suggest that the benefits may come partly from the antithrombotic properties of statins. Statins reduced the level of TAT, sP-selectin, sCD40L and P-selectin exposure at surface of platelets. Reduced levels of P-selectin at the platelet surface were associated with reduced platelet cholesterol content in subjects treated with statins. These studies suggest an early direct effect of statins on platelets and a late prolonged effect that is associated with progressive reduction of plasma LDL-cholesterol levels. Both the early and late effects are proposed to lower platelet activation and contribute to the reduced risk. Consistent with the idea that cholesterol enrichment increases platelet activation, infusions of a reconstituted HDL (rHDL) preparation

reduced *ex vivo* platelet activation in diabetic subjects, likely by promoting cholesterol efflux from platelets.

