Secondary measures – Secondary measures will include various cellular and circulating markers of platelet activation measured by flow cytometry or commercially-available enzyme-linked immunoassays (ELISAs). The target enrollment of 24 subjects should provide at least 80% power to detect differences between treatment groups based on data reported in the literature. For example, platelet P-selectin level measured by flow cytometry and reported as % positive cells (out of 50,000 cells counted) showed a mean reduction  $\pm$  SD of  $10.9 \pm 6.0$  (simvastatin),  $10.9 \pm 5.6$  (atorvastatin),  $7.2 \pm 6.8$  (fluvastatin) and  $9.0 \pm 6.8$  (pravastatin) following 30 days of statin treatment in hypercholesterolemic patients compared with untreated controls. In a separate study of stroke patients with hypercholesterolemia, platelet P-selectin showed a mean reduction of  $41 \pm 27\%$  positive cells in response to thrombin following 6 months of treatment with simvastatin compared to baseline measurements in the same subjects before statin treatment. An additional

effect of simvastatin treatment was observed for soluble P-selectin serum concentrations measured by ELISA. Soluble P-selectin showed a mean reduction of  $46.4 \pm 49$  ng/ml compared to baseline measurements in the same subjects before statin treatment. Other secondary measures include VerifyNow IIb/IIIa and VerifyNow Aspirin assays.

C. Study Design: Amgen will provide Evolocumab and placebo as open label. An independent biostatistician will generate a randomization table and provide it to Research Pharmacy of CUMC and Research Pharmacy will randomize the subjects accordingly. All patients recruited will start with placebo and blood and urine samples will be collected at day 7 and day 14. Then, the subjects will be randomized so that half will continue to receive placebo and half will receive Evolocumab via subcutaneous injection of 140 mg every 14 days. Blood and urine samples will be collected at day 21 and day 28. Then, all patients will receive Evolocumab 140 mg every 14 days and the treatment will continue.

Blood and urine samples will be collected following Evolocumab therapy at day 84 and 196 (Fig. 2). While every effort will be made to collect the blood and urine samples on the indicated time points, variation for the sample collection within 1-3 days at the indicated time point will be

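### The at-least-80% between-group power stated for the secondary markers rests on full statin effects, although the primary calculation halves the statin effect; two cited figures miss 80% even undiscounted, and none reaches it if the halving is extended

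*Combined protocol and SAP*

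**What the plan says.** All of this is in the combined protocol and SAP. Under Proposed studies, B. Power Calculation, the plan explains that its hypothesis rests on LDL lowering by evolocumab and that it borrows effect sizes from statin studies.

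- **Primary measure.** The cited statin effect is 102 PRU with SD 54. The plan then allows for a smaller effect: "Since the effects of statins on platelet aggregation may be mediated by both LDL-lowering and non-LDL-lowering mechanisms", it recalculates with half the difference, 51 PRU, and concludes: "Then, we estimate 11 subjects". An equal placebo group and an allowance for losses lead to 24. On method it says: "The sample size estimates have been run using one-group, paired t-test published data". The comparison of evolocumab with parallel placebo is assigned to a two-sided two-group t-test.
- **Secondary measures.** "The target enrollment of 24 subjects should provide at least 80% power to detect differences between treatment groups", by reference to published data. The examples are reductions in platelet P-selectin of 10.9 (SD 6.0, simvastatin), 10.9 (SD 5.6, atorvastatin), 7.2 (SD 6.8, fluvastatin) and 9.0 (SD 6.8, pravastatin); 41 (SD 27) in a stroke study; and a reduction in soluble P-selectin of 46.4 (SD 49) ng/ml. None is discounted, and no reason is given.
- **Introduction.** After listing TAT, soluble P-selectin, soluble CD40L and surface P-selectin as lowered by statins, it says: "These studies suggest an early direct effect of statins on platelets", alongside a later effect linked to falling LDL.

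**The concern.** The same section makes two different assumptions about how far a statin effect carries over to evolocumab. For PRU only half is credited, and that half sets the trial size. For the markers all of it is credited, and that supports the power statement. The stated reason for the discount, a possible non-LDL route, is not obviously peculiar to aggregation, since the Introduction describes a direct statin effect on platelets just after naming P-selectin among the markers lowered.

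At stake is how a negative marker result will be read. Section F says the marker results will help judge the validity of these markers for larger ongoing studies. It concedes limited power only for the genotype question. A reader who trusts at least 80% would give a null marker result more weight than the design may support.

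**Working it through.** **Inputs.** Alpha 0.05 two-sided, target power 0.80 and the two-group t-test come from the primary-measure text. Equal allocation comes from C. Study Design, so 24 subjects give 12 per arm; the 22 complete data sets required there give 11 per arm. Means and SDs are those listed above. My assumptions are that the cited SD applies in each arm and that placebo shows no mean change. The documents do not say more about these SDs.

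**Plan's own figure first.** For a paired t-test, d = mean/SD, noncentrality = d × √n, df = n − 1.
- 51/54 = 0.944: power is 75.7% at n = 10 and 80.6% at n = 11. The stated 11 is reproduced.
- 102/54 = 1.889: n = 5 already gives 88%. The stated 6 is slightly generous.

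**Between-group power for the markers.** d = f × mean/SD, where f is the fraction of the statin effect retained. Noncentrality = d × √(n/2), df = 2n − 2. At 12 per arm, df = 22, the critical t is 2.074 and √6 = 2.449. Example, pravastatin at full effect: d = 9.0/6.8 = 1.324, noncentrality 3.24, power 87.2%. Halved: d = 0.662, noncentrality 1.62, power 34.1%.

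| Cited figure | d (full) | Two-group, full | Two-group, 30% discount | Two-group, halved | Halved, 11 per arm | Paired n = 12, full | Paired n = 12, halved |
|---|---|---|---|---|---|---|---|
| Simvastatin 10.9/6.0 | 1.817 | 98.9% | 84.5% | 56.6% | 52.7% | >99% | 81.7% |
| Atorvastatin 10.9/5.6 | 1.946 | 99.5% | 89.0% | 62.5% | 58.4% | >99% | 86.6% |
| Pravastatin 9.0/6.8 | 1.324 | 87.2% | 58.3% | 34.1% | 31.5% | 98.6% | 55.2% |
| Fluvastatin 7.2/6.8 | 1.059 | 69.8% | 41.2% | 23.7% | 21.9% | 91.5% | 38.8% |
| Stroke study 41/27 | 1.519 | 94.4% | 70.2% | 42.8% | 39.6% | 99.7% | 66.9% |
| Soluble P-selectin 46.4/49 | 0.947 | 60.2% | 34.2% | 19.9% | 18.5% | 84.7% | 32.2% |

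Two-group columns are at 12 per arm unless marked.

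**Separating the two causes.** With full effects and the paired test, all six figures exceed 80%. Changing only the test, from paired to the two-group comparison that the sentence names, takes fluvastatin and soluble P-selectin below 80%. Applying the halving as well takes the other four below.

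**How much discount matters.** 80% power needs d = 1.197 at 12 per arm. Dividing by each full d gives the fraction of the statin effect that must be retained: atorvastatin 61.5%, simvastatin 66%, stroke study 79%, pravastatin 90%. Fluvastatin (113%) and soluble P-selectin (126%) would need more than the full effect.

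**Detectable difference at 80% power.** At 12 per arm, 1.197 × 5.6 = 6.7 and 1.197 × 6.8 = 8.1 percentage points. At 11 per arm, d = 1.256, giving 7.0 to 8.5 points.

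**The case against.** - **The discount is given for aggregation only, and tentatively.** The wording is that effects may be so mediated and that one can calculate on a halved difference. This stands. Extending 50% to P-selectin is an assumption made here, not a rule in the plan. A reader might infer that the plan holds evolocumab to lack the non-LDL routes, or that 50% is its general conversion from statins; it says neither.
- **The Introduction also points the other way.** It links lower surface P-selectin under statins to lower platelet cholesterol, and it describes a late effect tied to LDL. One cited P-selectin figure is at six months. This could support a smaller discount for platelet P-selectin, but the power section does not use it to justify omitting one.
- **The result depends on the size of the discount.** This stands. At 30%, simvastatin and atorvastatin stay above 80%, so the statement that no figure reaches 80% holds for the halving and not for every discount.
- **Part of the shortfall is a separate defect.** This stands. The sizing is paired and the promise is between groups; the halved primary effect (51/54) itself has only 60% two-group power at 12 per arm. The paired method does not rescue the statement under halving, however: only simvastatin and atorvastatin then exceed 80%, and the sentence concerns differences between treatment groups.
- **The figures are examples from the literature for secondary measures.** True, but they are the only support offered for an explicit power level.

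**Conclusion.** The general statement of at least 80% between-group power is not supported. At full statin effects, power runs from 60% to 99.5% and two of the six cited figures miss 80%; that part comes from the paired-versus-two-group mismatch and needs no discount. If the plan's halving for aggregation is extended to the markers, power falls to about 20% to 62.5% (18% to 58% at 11 per arm) and no cited figure reaches 80%. With a 30% discount, two of six do.

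The defect is an unexplained difference in assumptions, together with a test mismatch. It should not be read as proof that the plan contradicts itself arithmetically, or that true power for P-selectin is the halved figure; the right discount for these markers is not given in the documents. Nor do the documents say that a null marker result would be taken as evidence of no effect; that is a risk, not a stated intention. The figures rest on the cited SDs applying in each arm, no mean change on placebo, and equal arms.

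**What to change.** In the Secondary measures paragraph of B. Power Calculation, do one of the following:

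1. Replace the 80% statement with two-group power at 12 per arm under both the full effect (about 60% to 99.5%) and the halved effect (about 20% to 62.5%), noting that the halving is carried over from the aggregation calculation; or
2. Explain why the discount does not apply to these markers, and state the full-effect range.

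In either case, add the difference detectable with 80% power (about 1.2 SD at 12 per arm, 1.26 SD at 11; for platelet P-selectin roughly 6.7 to 8.1 percentage points at 12 per arm with SD 5.6 to 6.8). Say that a non-significant secondary marker is inconclusive.

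The cost is one rewritten paragraph and a less favourable stated figure. Enrolment does not change.

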allowed. The power of this design is that we can compare any changes due to Evolocumab therapy relative to a placebo control.

Based on the power calculations as detailed above, recruitment of total 20 participants into this study will give ~80% power for statistical significance of 0.05. We target to recruit 24 subjects over 2 year period. However, we anticipate that some participants will drop out from the study and incomplete data will be obtained. We will continue to recruit the subjects until the complete data sets for 22 subjects are obtained. Incomplete data from the dropout may not be used unless data up to 28 days at least are collected.

D. Genotyping: rs3184504 genotyping will be performed using the genomic DNA samples

and rs3184504 specific PCR genotyping primers from Invitrogen.

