- E. Assays: We propose to use a clinically validated system, VerifyNow, as the assay for assessment of platelet activation state. Compared with other assays, this system requires ~2 ml whole blood, with minimal ex vivo manipulations, minimal hands-on time and no pipetting or sample preparation. It is fast (10 min for result presentation) and approved as a clinical lab test of platelet reactivity. Thus, the results obtained this way should be more reliable when the data need to be compared with results from other studies using the same assay. In principle, this assay is designed to measure platelet function based upon the ability of activated platelets to bind fibrinogen. Fibrinogen-coated microparticles aggregate in whole blood in proportion to the number of unblocked platelet GP IIb/IIIa receptors. Light transmittance increases as activated platelets bind and aggregate fibrinogen-coated beads. The instrument measures this change in optical signal caused by aggregation. We propose to use VerifyNow IIb/IIIa, VerifyNow PRUtest, and VerifyNow Aspirin assays, testing platelet responses to thrombin-like peptide, ADP and arachidonic acid, respectively. In addition to the VerifyNow assay, basal level of P-selectin and active form of GPIIb/IIIa at surface of platelets will be determined by flow cytometry. In order to reduce the variation generated by manipulation of blood samples in vitro, we will use 1% paraformaldehyde to fix an aliquot of the whole blood sample and basal levels of P-selectin and active GPIIb/IIIa at surface of platelets will be determined by flow cytometry after staining with specific P-selectin or PAC-1 antibody (PAC-1 specific for active GPIIb/IIIa). Plasma levels of TAT, sP-selectin and sCD40L will be determined by ELISA assays. Levels of plasma LDL cholesterol, HDL cholesterol, triglyceride and platelet total cholesterol content will be determined. All these assays are validated assays.

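### The plan's own soluble P-selectin figure gives about 60% between-group power at 12 per arm (56% at 11), not 80%, if the placebo SD equals the cited 49 ng/ml

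*Combined protocol and SAP*

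**What the plan says.** All references are to the combined protocol and SAP.

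- **Section B, secondary measures.** The target of 24 subjects "should provide at least 80% power to detect differences between treatment groups". Six literature figures follow. Four are reductions in platelet P-selectin (% positive cells) under different statins, described as "following 30 days of statin treatment in hypercholesterolemic patients compared with untreated controls". One is a thrombin-stimulated platelet P-selectin reduction after 6 months of simvastatin. One is soluble P-selectin, 46.4 ± 49 "ng/ml compared to baseline measurements in the same subjects before statin treatment".
- **Section B, primary measure.** "Between-group thirty day evolocumab treatment will be tested by standard two-group t-test", two-sided. On sizing: "The sample size estimates have been run using one-group, paired t-test published data". An equal number of subjects is then added for placebo.
- **Section C.** Half of the subjects are randomised to each arm, and "We will continue to recruit the subjects until the complete data sets for 22 subjects are obtained". That is 12 per arm at the enrolment target and 11 per arm with complete data.
- **Section E.** "Plasma levels of TAT, sP-selectin and sCD40L will be determined by ELISA assays". Platelet-surface P-selectin is to be measured at its basal level.

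**The concern.** The power statement concerns a comparison between arms, but the soluble P-selectin figure behind it is a before-and-after change in one treated group. A paired test on such data carries the sampling error of one mean. A two-group comparison carries the error of two. Adding a placebo group of equal size does not carry the paired power over to the between-group test.

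Soluble P-selectin is the only circulating marker for which the plan gives a figure. Section F says the results will help judge the validity of these markers for larger studies. A reader who trusts the 80% statement could take a null result as evidence against the marker when the trial had a much larger chance of missing the effect than stated.

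**Working it through.** **Inputs.** Reductions and SDs: section B, secondary measures. Two-sided two-group t-test and alpha 0.05: section B, primary measure; assumed to apply to the secondary measures, for which no test or alpha is named. Per-arm numbers 12 and 11: section C. Assumed because the plan does not say: mean placebo change of zero, and placebo SD equal to the cited SD.

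**Step 1: reproduce the plan's own sizing.** One-group paired test: df = n − 1, noncentrality = d√n. For the primary, d = 51/54 = 0.944. Power is 75.7% at n = 10 and 80.6% at n = 11, which matches the plan's 11. For d = 102/54, n = 5 already gives 87.8%; the plan's 6 gives 95.4%. The plan's method is therefore the paired test, as it says.

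**Step 2: soluble P-selectin in the paired test.** d = 46.4/49 = 0.947.
- n = 12: noncentrality 0.947 × √12 = 3.28, critical t (11 df) 2.201, power 84.7%.
- n = 11: noncentrality 0.947 × √11 = 3.14, critical t (10 df) 2.228, power 80.8%.

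The paired test therefore supports 80%, but only for a within-arm change.

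**Step 3: the same figure between groups.** df = 2n − 2, noncentrality = d√(n/2).
- 12 per arm: 0.947 × √6 = 2.32, critical t (22 df) 2.074, power **60.2%**.
- 11 per arm: 0.947 × √5.5 = 2.22, critical t (20 df) 2.086, power **56.1%**.

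More lenient calculations do not close the gap. At 12 (11) per arm, the normal approximation gives 64.0% (60.3%) and a one-sided test 72.7% (69.1%). On the two-sided t-test, 80% would take 19 per arm (81.1%; 18 gives 78.8%).

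**Step 4: all six figures.** Cited SD in both arms, two-sided 0.05.

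| Cited figure | Reduction ± SD | d | Two-group, 12 (11) per arm | Paired, n = 12 (11) |
|---|---|---|---|---|
| Soluble P-selectin | 46.4 ± 49 | 0.947 | 60.2% (56.1%) | 84.7% (80.8%) |
| Fluvastatin | 7.2 ± 6.8 | 1.059 | 69.8% (65.6%) | 91.5% (88.5%) |
| Pravastatin | 9.0 ± 6.8 | 1.324 | 87.2% (83.9%) | 98.6% (97.6%) |
| Thrombin-stimulated | 41 ± 27 | 1.519 | 94.4% (92.3%) | 99.7% (99.5%) |
| Simvastatin | 10.9 ± 6.0 | 1.817 | 98.9% (98.2%) | >99.9% (>99.9%) |
| Atorvastatin | 10.9 ± 5.6 | 1.946 | 99.5% (99.1%) | >99.9% (>99.9%) |

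**Step 5: sensitivity to the placebo SD.** Soluble P-selectin, treated SD fixed at 49, pooled t-test, 1,000,000 simulated trials per cell.

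| Placebo SD (ng/ml) | 12 per arm | 11 per arm |
|---|---|---|
| 12.25 | 85.7% | 82.2% |
| 18 | 83.4% | 79.9% |
| 24 | 80.2% | 76.4% |
| 30 | 76.2% | 72.2% |
| 36.75 | 70.8% | 66.6% |
| 49 | 60.2% | 56.1% |
| 61.25 | 50.0% | 46.5% |

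**Step 6: what the design can detect.** Two-group power of 80% needs d = 1.197 at 12 per arm and 1.256 at 11. At SD 49 that is 1.1968 × 49 = 58.6 ng/ml and 1.2560 × 49 = 61.5 ng/ml, against the cited 46.4. Equivalently, a common SD would have to be at most 46.4/1.197 = 38.8 (46.4/1.256 = 36.9) ng/ml, which is 21% (25%) below 49.

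**The case against.** The strongest objection is that the answer turns on a number the plan does not contain. The 49 comes from treated patients and may include variation in drug response that a placebo arm would lack. Over the range in step 5, power runs from about 46% to 86%. This stands as a limit on the precise value, and the 56–60% must always carry its equal-SD condition. It does not rescue the plan's sentence: 80% at 12 per arm needs a placebo SD of about half the cited one, and nothing in the plan supports that.

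Other points on that side:

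- **No test is named for the secondary measures, and two samples are taken before and two after randomisation.** If each pair were averaged, compound symmetry would reduce the SD of change to 49/√2 = 34.6 ng/ml and power would be about 88% (85%). But the plan does not state such averaging, and a comparison between treatment groups cannot be a one-group paired test.
- **The figures are offered as examples, and four of six support the claim.** True, but the sentence is general and one of its own examples does not support it.
- **The ± 49 is not itself labelled an SD.** Fair. Reading it as an SD is the natural inference; a standard error would imply a larger SD and lower power. For fluvastatin the text compares with untreated controls and does not say what the SD describes, so that result is weaker evidence.
- **The cause lies in the primary sizing.** The primary's 51/54 has the same gap, 59.9% (55.9%) in a two-group test. That is a reason to correct both places, not to leave this one.

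**Conclusion.** The concern holds. The statement of at least 80% between-group power is not supported by all the figures cited for it. For soluble P-selectin the power is about 60% at 12 per arm and 56% at 11, so an effect of the cited size would be missed about 40–44% of the time instead of at most 20%. This rests on a two-sided two-group t-test at 0.05, no mean placebo change, ± 49 read as the SD of change, and the same SD on placebo. Fluvastatin falls short on the same basis; the other four figures do not.

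Two of the cited figures also differ from what will be measured. The text reports that an "effect of simvastatin treatment was observed for soluble P-selectin serum concentrations measured by ELISA", whereas section E specifies plasma. The thrombin-stimulated figure is not the basal platelet P-selectin of section E. These mismatches do not alter the powers above, but they weaken the figures as support. The effect on the trial is limited to how the secondary results are read.

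**What to change.** In section B, secondary measures, replace the general 80% sentence with wording that:

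- gives the detectable standardised difference at 80% power: about 1.20 with 12 per arm and 1.26 with 11 per arm, two-sided two-group t-test at 0.05;
- gives soluble P-selectin power as about 56–60%, naming the test and the assumptions of equal SDs and no placebo change, ideally with the range over placebo SDs;
- limits any 80% claim to the cited figures that support it;
- does not use the thrombin-stimulated figure as support for the basal P-selectin measure, and notes that the soluble P-selectin figure is a serum value.

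If averaging of the paired visits is intended, the plan should say so and state the power on that basis. The cost is wording only, with no extra patients or assays. The stated power becomes less favourable.
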